9.3 SERIOUS ADVERSE EVENT REPORTING

The Principal Investigator or its representative will be responsible for telephone or fax reporting of any unexpected SAEs to the FDA. The Principal Investigator or its representative will notify the FDA by telephone or fax of any fatal or life threatening experience (expedited report) associated with the use of the study therapy as soon as possible but no later than seven calendar days after receipt of the information. Initial notification will be followed by a written report within 15 calendar days. For SAEs associated with the use of the study therapy, the Principal Investigator will notify the FDA as soon as possible, but no later than 15 days, of the initial receipt of the information. The Principal Investigator or Sub-Investigator is responsible for informing the Institutional Review Board (IRB) and DSMB of any study related and unexpected SAEs.

9.4 ELICITING ADVERSE EVENT INFORMATION

In addition to research participant observations, AEs will be documented from any data collected throughout the study including clinically significant laboratory values or physical exam findings.

9.5 STOPPING GUIDELINES

The following stopping guidelines will be monitored during the duration of the study. The stopping guidelines will be monitored by the study team and are to be used to indicate boundaries requiring discussion by the investigators and DSMB. The study will be stopped for a safety review if:

- Any participant experiences a grade 4-5 infusion reactions within 48 hours of infusion; OR
- Two or more grade 4-5 adverse events determined to be temporally related to the study product by the medical safety monitor and/or the DSMB occur; OR
- Any participant experiences a blood stream infection within 6 months of infusion; OR
- Any participant develops grade II-IV GvHD; OR
- Any death.

A consensus decision to stop the study will be made by the investigators and the DSMB. Such a decision with its supporting documentation and possible future plans for the study will be submitted to, and discussed with, the FDA.

9.6 PARTICIPANT REPLACEMENT

In the event that any enrolled participants do not receive treatment, additional participants may be randomized in order to reach the target number of evaluable, treated participants.

10.0 DATA SAFETY MONITORING BOARD (DSMB)

A DSMB will be formed and a charter established. Members of the DSMB will be independent of Duke University and comprised of a minimum of three members, including a clinician with experience in the treatment of ASD and a physician with experience in cell therapy. The DSMB will be notified immediately for all SAEs directly related to the study product throughout the study. A total safety assessment will be prepared on an annual basis and forwarded to the DSMB for review as well. The DSMB and its members will have the right to make decisions and act independently. Policies of the DSMB will be described in the DSMB charter and signed by all members.

All study related and unexpected SAEs reported or observed during the study beginning at the time of the study infusion must be recorded and maintained in the study participant's paper files. Severe adverse infusion reactions (fatal, life threatening or requiring hospitalization) will be reported to the IRB and FDA in accordance with HRPP policies.

11.0 DATA HANDLING AND QUALITY ASSURANCE

11.1 CASE REPORT FORMS

As part of the responsibilities assumed by participating in the study, the Principal Investigator or Sub-Investigators agree to maintain adequate case histories of the research participants treated as part of the research under this protocol. The Principal Investigator or Sub-Investigator agrees to maintain accurate CRFs and source documentation as part of the case histories. Duke University will supply the CRF electronically (eCFR) through secured electronic data entry systems.

11.2 VIDEO AND AUDIO RECORDINGS

Video recordings of potential participants from parents and guardians may be submitted and used for determining study eligibility. Audio and video recordings may also be obtained of portions of the evaluations and interviews if indicated with parental consent, and may include full facial features and audio. The recordings will be used solely for analysis by the research team or for educational purposes if consent is obtained from the parent/guardian. They will be stored electronically on a password-protected server and identified by the participants' study ID. Software used to conduct and record visit assessments completed remotely will be done on Duke approved platforms and participants will receive instructions to enhance privacy and security measures.

11.3 INSPECTION OF RECORDINGS

The Principal Investigator or Sub-Investigators and institutions involved in the study will permit study-related monitoring, audits, IRB review, and regulatory inspection(s) by providing direct access to all study records. In the event of an audit, the Principal Investigator or Sub-Investigator agrees to allow the Food and Drug Administration (FDA) or other regulatory agency access to all study records. The Principal Investigator or Sub-Investigators should promptly notify all relevant parties of any audits scheduled by any regulatory authorities and promptly forward copies of any audit reports received to the both.

11.4 STUDY RECORD RETENTION

Study results will be retained in the participant's research record for six years after the study is completed or until the participant reaches the age of 21, whichever is longer. Essential documents should be retained until at least two years after the last approval of a marketing application in an International council for Harmonisation (ICH) region and until there are no pending or contemplated marketing applications in an ICH region or at least two years have elapsed since the formal discontinuation of clinical development of the investigational product. These documents should be retained for a longer period, however, if required by the applicable regulatory requirements.

11.5 Process for adding the Study Diagnostic Report to Patient's Duke Medical Record

As part of this study, it the participant (or their LAR, as applicable) also receives clinical services at Duke outside of the study, they may request have their clinical evaluation report(s) added to their Duke Maestro chart. Doing this will allow researchers and clinicians at the Duke Center for Autism and Brain Development to better integrate our research and clinical programs. If the patient is getting care outside of the study at Duke, they may benefit from this by making clinical evaluations and care in the non-research context more seamless, allowing providers to review reports from clinical assessments conducted as part of the study in order to inform clinical care, and avoiding unnecessary duplication of efforts on the part of both research participant and study team. Most participants of the study are not patients receiving regular medical care at Duke outside of the study. However, in the event that a participant would like to have the report added to the medical record, they may make a request to do so.

When receiving a request, the study team will let the participant know, or remind them, that the diagnostic report will summarize diagnoses, developmental function, and cognitive skills and other symptoms and abilities that were assessed as part of the study; that we will not "list" or change diagnoses in the medical record, but will make the report available for other Duke Health providers to review. We will also note that the report will indicate that the individual received the evaluation as part of a study. Documentation of requests will be stored with the participant's research record.

11.6 Participant Engagement

Participants of this study may be contacted after their study participation to share their perspective and opinions on their study experience, including any parts that they enjoyed and/or any challenges. They will be reassured that this is completely optional. Questions include: their experience in the study generally, their opinion on research study assessments, the quality of print materials and interactions with our staff, anything about the study they found helpful and any challenges encountered, and what changes might be helpful to consider in the future. Interviews may be recorded on Duke-approved platforms if the family agrees. These open-ended questions and responses will not be asked as a part of this study, or used for data analysis, or to make conclusions about the study, but may be used in efforts to support the Duke Center for Autism and Brain Development's efforts in connecting with the broader community via social media, conferences, newsletters, seminars and other events/media about our research efforts and impact at the Duke Center for Autism. This activity will be key to the Center's efforts in promoting active engagement and bidirectional exchange with the families we serve and the broader community. These interviews may also help inform designing protocols and/or making changes as needed to enhance inclusivity, cultural appropriateness, and feasibility. If staff perform post-study interviews, participants will be asked whether they want to publish their identity in any publicly published information or would prefer to not be named. The relevant information will be added to a HIPAA waiver provided by the News office and authorization will be obtained through signing of the HIPAA waiver. Although these interviews and dissemination and outreach core (DOC) activities are not part of the study, we wish to inform the IRB that these interactions may take place as it may entail additional interactions with research participants.

Additionally, participants who are willing to have their image(s) or video(s) (including voice) used for purposes of media, news, trainings, articles, conferences and other dissemination activities, will also be asked to sign the appropriate HIPAA waiver provided by the DUHS News office with their selections and permissions noted in the form.

12.0 ADMINISTRATIVE ASPECTS

The following administrative items are meant to guide the Principal Investigator or Sub-Investigator in the conduct of the study but may be participant to change based on industry and government Standard Operating Procedures or Working Practice Documents or Guidelines.

12.1 CONFIDENTIALITY

All laboratory specimens, evaluation forms, reports, and other records will be identified in a manner designed to maintain research participant confidentiality. All records will be kept in a secure storage area with limited access. Clinical information will not be released without the written permission of the research participant's guardian except as necessary for monitoring and auditing.

The Principal Investigator or Sub-Investigator and all employees and coworkers involved with this study may not disclose or use for any purpose other than performance of the study, any data, record, or other unpublished, confidential information disclosed to those individuals for the purpose of the study.

12.2 INSTITUTIONAL REVIEW BOARD APPROVAL

Federal regulations and the ICH guidelines require that approval be obtained from an IRB prior to participation of human research participants in research studies. Prior to the study onset, the protocol, informed consent, any advertisement used to recruit study participants, and any other written information regarding this study to be provided to the research participant or the research participant's legal guardian must be approved by the IRB.

All IRB approvals should be signed by the IRB Chairman or designee and must identify the IRB name and address, the clinical protocol by title and/or protocol number, and the date the approval and/or favorable opinion was granted.

The Principal Investigator or Sub-Investigator is responsible for obtaining continued review of the clinical research at intervals not exceeding one year or otherwise specified by the IRB. The Principal Investigator or Sub-Investigator must supply the Sponsor or its designee with written documentation of continued review of the clinical research.

12.3 MODIFICATION OF THE PROTOCOL

Any changes in this research activity, except those necessary to remove an apparent, immediate hazard to the research participant, must be reviewed and approved by the IRB.

12.4 INFORMED CONSENT

A written informed consent in compliance with Part 50 of Title 21 of the Code of Federal Regulations (CFR) and Institutional IRB shall be obtained from each research participant prior to entering the study or performing any unusual or non-routine procedure that involves risk to the research participant.

Before enrollment, each prospective research participant and/or at least one legal guardian will be given a full explanation of the study and be allowed to read the approved informed consent form.

Once the Principal Investigator or Sub-Investigator is assured that the research participant/legal guardian understands the implications of participating in the study, the research participant/legal guardian will be asked to give consent to participate in the study by signing the informed consent form.

The Principal Investigator or Sub-Investigator shall provide a signed/dated copy of the signed informed consent to the research participant and/or legal guardian.

12.5 PROTOCOL VIOLATIONS AND DEVIATIONS

The Principal Investigator or Sub-Investigator or designee must document and explain in the research participant's source documentation any deviation from the approved protocol. The Principal Investigator or Sub-Investigator may implement a deviation from, or a change of, the protocol to eliminate an immediate hazard to study research participants without prior IRB approval. As soon as possible after such an occurrence, the implemented deviation or change, the reasons for it, and any proposed protocol amendment(s) should be submitted to the IRB for review and approval, to the Sponsor for agreement, and to the regulatory authorities, if required.

A deviation from the protocol is an unintended and/or unanticipated departure from the procedures and/or processes approved by the Sponsor and the IRB and agreed to by the Principal Investigator or Sub-Investigator. Deviations usually have an impact on individual research participants or a small group of research participants and do not involve inclusion/exclusion or primary endpoint criteria. A protocol violation occurs when there is non-adherence to the protocol that results in a significant, additional risk to the research participant, when the research participant or Principal Investigator or Sub-Investigator and the research participant, when the research participant or Principal Investigator or Sub-Investigator has failed to adhere to significant protocol requirements (inclusion/exclusion criteria) and the research participant was enrolled without prior Sponsor approval, or when there is non-adherence to FDA regulations and/or ICH GCP guidelines.

Protocol violations and deviations will be documented by the study coordinator and the clinical monitor will notify study staff and update protocol deviation documentation throughout the course of monitoring visits. Principal Investigators or Sub-Investigators will be notified of violations and/or deviations in writing by the study coordinator and/or the study monitor. The IRB should be notified of all protocol violations and deviations meeting criteria in a timely manner as required by the site's IRB.

12.6 STUDY REPORTING REQUIREMENTS

By participating in the study, the Principal Investigator or Sub-Investigator agrees to submit reports of serious adverse events according to the timeline and method outlined in the protocol. In addition, the Principal Investigator or Sub-Investigator agrees to submit annual reports to his/her IRB as appropriate. The Principal Investigator or Sub-Investigator also agrees to provide the Sponsor with an adequate report shortly after completion of the Principal Investigator's or Sub-Investigator's participation in the study.

12.7 FINANCIAL OBLIGATIONS

Duke University is not financially responsible for further testing/treatment of any medical condition that may be detected during the screening progress. In addition, in the absence of specific arrangements, Duke University is not financially responsible for further treatment of the research participant's disease.

12.8 STUDY CONDUCT

The Principal Investigator agrees that the study will be conducted according to the principles of the ICH E6 Guideline on GCP and the principles of the World Medical Association Declaration of Helsinki. The Principal Investigator will conduct all aspects of this study in accordance with all national, state, and local laws or regulations.

12.9 PUBLICATIONS

Following completion of the study, the data may be considered for reporting at a scientific meeting or for publication in a scientific journal. In these cases, Duke University will be responsible to determine how the manuscript is written and edited, the number and order of authors, the publication to which it will be submitted, and other related issues.

14.0 APPENDIX 1: SAFETY QUESTIONNAIRE

BASELINE MEDICAL & BEHAVIORAL HISTORY QUESTIONNAIRE

Please tell us if your child has ever experienced any significant problems with any of the following conditions using the column marked EVER. If so, tell us whether they have continued to experience significant problems with that condition during the past 2 months in the next column.

		EV	EVER		st 2 nths
		No	Yes	No	Yes
1	Has your child ever had any fevers with no clear cause?				
2	Has your child ever had any serious or recurrent infections?				
3	Has your child ever had any allergic reactions?				
4	Has your child ever had significant problems with autoimmune disorders?				
5	Has your child ever had any significant problems with rashes or abnormal skin lesions?				
6	Has your child ever had jaundice (yellowing of the skin or eyes), except as a newborn?				
7	Has your child ever received a blood transfusion?				
8	Has your child ever had any significant problems with bloody noses, easy bruising or prolonged bleeding?				
9	Has your child ever had any abnormal blood tests?				
10	Has your child ever had any problems with breathing, asthma or coughing?				
11	Has your child ever had any problems that make you concerned about his/her heart?				
12	Has your child ever had any significant problems with his/her mouth or teeth?				
13	Has your child ever had any bowel problems, including any bowel accidents?				
14	Does your child have ongoing problems with diarrhea?				
15	Has your child ever had any ongoing episodes of vomiting?				
16	Has your child ever had any significant problems with appetite?				
17	Has your child ever had any significant problems with weight?				
18	Has your child ever had any significant problems with his/her muscles or joints?				
19	Has your child ever had any problems with swelling in any part of his or her body?				
20	Has your child ever had any problems with his/her urinary tract or problems when he/she urinates?				
21	Has your child ever had any problems with his/her breasts/nipples or private parts?				
22	Has your child ever had any problems with how thirsty he or she is?				
23	Has your child ever had any problems with his/her ears or hearing?				
24	Has your child ever had any eye or vision problems?				
25	Has your child ever had problems with severe or frequent headaches?				

		EV	EVER		st 2 nths
		No	Yes	No	Yes
26	Has your child ever had any significant problems with dizziness?				
27	Has your child ever had any seizures?				
28	Has your child ever had any problems with involuntary movements?				
29	Is your child chronically tired or fatigued?				
30	Has your child ever had cancer?				
31	Has your child ever had a tumor?				
32	Has your child ever had any unexplained masses or growths?				
33	Have you ever had any other concerns about your child's medical health? If so, please explain below.				
34	Has your child ever had any significant problems sleeping at night?				
35	Has your child ever had any significant problems being too sleepy during the day?				
36	Has your child ever had differences in sensory processing such as sensory seeking behaviors or sensory aversion behaviors (including food aversion)?				
37	Has your child ever had any problems with rituals, being flexible, repetitive behaviors or repetitive language?				
38	Has your child ever had any problems with hyperactivity or impulsivity?				
39	Has your child ever had any significant problems with refusing to follow directions that he/she understands?				
40	Has your child ever had any significant problems with aggression, irritability or getting frustrated easily?				
41	Has your child ever had significant problems (more frequent/severe than other kids) with meltdowns or agitation?				
42	Has your child ever had any problems with staying motivated?				
43	Has your child ever had ever any problems with worries or sadness?				
44	Has your child ever had any problems with hurting him/herself on purpose or wanting to die?				
45	Has your child ever had any significant problems with mood swings?				
46	Has your child ever had any problems with believing things that aren't true or seeing/hearing things that aren't there?				
47	Has your child ever had any problems with seeming not to know where he/she was or what was really happening?				
48	Have you ever had any other concerns about your child's behavior, which is not addressed in questions 33-45? If so, please explain below.				

Please use the space below to explain any "yes" answers.

FOLLOW-UP MEDICAL & BEHAVIORAL HISTORY QUESTIONNAIRE

Please tell us if your child has ever experienced any significant problems with any of the following conditions SINCE YOU LAST COMPLETED THIS QUESTIONNAIRE.

		Pas mor	
		No	Yes
1	Has your child had any fevers?		
2	Has your child had infections?		
3	Has your child had any allergic reactions?		
4	Has your child had any new or worse problems with autoimmune disorders?		
5	Has your child had any new rashes or abnormal skin lesions?		
6	Has your child developed jaundice (yellowing of the skin or eyes)?		
7	Has your child received a blood transfusion?		
8	Has your child had any new problems with bloody noses, easy bruising or prolonged bleeding?		
9	Has your child had any abnormal blood tests since their last visit?		
10	Has your child had any new or worsening problems with breathing, asthma or coughing?		
11	Has your child had any new or worsening problems with their heart?		
12	Has your child had any new problems with his/her mouth or teeth? (Do not include losing baby teeth.)		
13	Has your child had any new or worsening bowel problems, including bowel accidents?		
14	Has your child had any new or worsening diarrhea?		
15	Has your child had any new or worsening episodes of vomiting?		
16	Has your child had any new or worsening problems with appetite?		
17	Has your child had any new or worsening problems with weight?		
18	Has your child had any new or worsening problems with his/her muscles or joints?		
19	Has your child had any new or worsening swelling in any part of his or her body?		
20	Has your child had any new or worsening problems when he/she urinates?		
21	Has your child had any new or worsening problems with his/her breasts/nipples or private parts?		
22	Has your child had any changes in thirstiness?		
23	Has your child had any new or worsening problems with his/her ears or hearing?		
24	Has your child had any new or worsening eye or vision problems?		
25	Has your child had any new or worsening headaches?		
26	Has your child had any new or worsening problems with dizziness?		
27	Has your child had any new or worsening seizures?		
28	Has your child had any new or worsening problems with involuntary movements?		
29	Has your child had any new or worsening chronic tiredness or fatigue?		

		Pas	st 3
		mor	nths
		No	Yes
30	Has your child ever had cancer?		
31	Has your child ever had a tumor?		
32	Has your child ever had any unexplained masses or growths?		
33	Has your child been hospitalized? If so, please explain below.		
34	Has your child had any new significant injuries?		
35	Have you ever had any other concerns about your child's medical health? If so, please explain below.		
36	Has your child had any new or worsening problems sleeping at night?		
37	Has your child had any new or worsening problems being too sleepy during the day?		
38	Has your child had any new or worsening problems with differences in sensory processing such as sensory seeking behaviors or sensory aversion behaviors (including food aversion)?		
39	Has your child had any new or worsening problems with rituals, being flexible, repetitive behaviors or repetitive language?		
40	Has your child had any new problems with hyperactivity or impulsivity?		
41	Has your child had any new or worsening problems with refusing to follow directions that he/she understands?		
42	Has your child had any new or worsening problems with aggression, irritability or getting frustrated easily?		
43	Has your child had any new or worsening with meltdowns or agitation?		
44	Has your child had any new or worsening problems with staying motivated?		
45	Has your child had any new or worsening problems with worries or sadness?		
46	Has your child had any new or worsening problems with hurting him/herself or wanting to die?		
47	Has your child had any new or worsening problems with mood swings?		
48	Has your child had any new or worsening problems with believing things that aren't true or seeing/hearing things that aren't there?		
49	Has your child had any new or worsening problems with knowing where he/she is or who is with him/her?		
50	Has your child had any new or worsening problems with their thinking?		
51	Have there been any other new or worsening problems with your child's behavior, which is not addressed in questions 35-50? If so, please explain below.		

Please use the space below to explain any "yes" answers.

Open Label Phase I HCT-MSC in Toddlers with ASD (TACT)

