6.6 SAFETY FOLLOW-UP

On Day 1 following each infusion, the participant will be evaluated by study staff to assess for any infusion related adverse reactions or complications. This assessment can be done in person, over

the phone, by email or a teleconference. At 7-10 days post each infusion, a member of the study team will contact the parent or guardian via phone, teleconference, or email to assess patient status and any adverse events. A questionnaire (see Appendix 1) will be administered at each subsequent visit and at 3, 9 and 12 months to assess for serious adverse events. PRA will be obtained pre-treatment and at 6 and 12 months after the initial infusion.

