Pediatric Quality of Life (PedsQL) 4.0 Generic Core Scales: The PedsQL 4.0 Generic Core Scales is a 5-minute parent questionnaire that measures the child's functioning in the dimensions of: physical, emotion, social and school. The Toddler Parent Report version is composed of 21 items and will be completed at the baseline and 6 month visits and remotely at 12 months.

Center for Autism and Brain Development (CABD) Demographics Form: The CABD demographics form collects race and ethnicity according to the NIH reporting standards. Additional questions collect data to help characterize the population. This parent questionnaire takes less than 10 minutes to complete and will only be completed at the baseline visit.

Medical and Behavioral History Questionnaire (MBHQ): The MBHQ is a broad assessment of medical and behavioral issues. It is completed at baseline, three, six, nine and 12 months.

COVID-19 Exposure and Family Impact Survey (CEFIS): ¹⁰¹ The CEFIS is an open-source parent report questionnaire that conceptualizes exposure to potentially traumatic aspects of COVID-19 and assesses the impact of the pandemic on the family. The CEFIS will be completed every three months. Data collected with the CEFIS measure will be de-identified and shared with the tool developers through a CSV file sent securely using DukeBOX.

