7.6 REQUIRED EVALUATIONS

7.6.1 Medical and Safety Assessments:
			Time Points [#]		
	Screening	Baseline (Visit 1)	7-10 days post-infusion	6 months	12 months
CBCD*, CMP*, participant HLA, fragile X, CMA/WES	х				
Review of prior records ± videos	Х				
History & Physical		Х		Х	
Samples for storage of DNA & viable mononuclear cells, DNA extract and hold		х			
Donor Referral Panel		Х			
CBCD, CMP, HLA Antibody Screen (PRA), Immune Reconstitution Panel, Humoral Immune Profile		X*		х	х
Neuropsychological evaluation		Х		Х	Х
Safety Assessment –in person (Day post-infusion)		х			
Safety Assessment – phone call/survey			Х		

*CBCD, CMP, PRA may be obtained at initial visit or within 6 months prior to consent; HLA, fragile X, CMA/WES any time prior to enrollment. Safety and return assessments should be performed within a month of the indicated time point.

7.6.2 Diagnostic, Behavioral, Cognitive/Language, and Attention evaluations.

	Measure	Time (min)	Baseline	3 mo.	6 mo.	9 mo.	12
Clinician	Brief Observation of Symptoms of	45-60	Х				
Assessme	Autism (BOSA)						
nt w/ Child	Developmental Assessment of Young	45-60	Х				
	Children – Second Edition (DAYC-2)						
Other							
Assessme							
nts w/	SenseToKnow (S2K) app	10	Х		Х		
Child	Demost Ohild latens sting (DOI) for JEDI	40	V		X		
Observatio n of child	Parent-Child Interaction (PCI) for JERI	12	Х		Х		
n of child	rating						
Caregiver	Vineland Adaptive Behavior Scales,	60-120	Х		Х		Х
Interviews	Third Edition Survey Interview Form	00-120	^		^		^
interviews	Clinical Global Impression Parent	30-45	Х		Х		
	Interview	30-43	X				
-	Medical/Behavioral History	15-30	Х	Х	Х	X	Х
	Questionnaire (MBHQ)	10 00	~				
Caregiver	Pervasive Developmental Disorder	30-45	Х	Х	Х	Х	Х
Questionn	Behavior Inventory (PDDBI)						
aires	Intervention History	15	Х	Х	Х	Х	Х
(Conducte	MacArthur-Bates Communicative	20-40	Х	Х	Х		Х
d with the	Development Inventories, Second						
Caregiver	Edition (CDIs)						
Only)	COVID-19 Exposure and Family	15	Х	Х	Х	Х	Х
	Impact Survey (CEFIS)						
	Pediatric Quality of Life (PedsQL)	5-10	Х		Х		Х
	Demographic Form	10	Х				
	Clinical Global Impression – Severity	15	Х		Х		
	(CGI-S)						
	Clinical Global Impression –						
	Improvement (CGI-I)						
Other	Diagnostic Statistical Manual-5 (DSM-	3-5	Х				
Clinician	5) Checklist						
Completed		0.5	X		X		
	Clinical Global Impressions - Severity	3-5	Х		Х		

Clir	nical Global Impressions -	3-5		Х	
Imp	provement				

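### The follow-up safety questionnaire states conflicting look-back periods, so a late or missed form can leave time unasked and an early form can report the same event twice.

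*Combined protocol and SAP*

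**What the plan says.** Section 6.6 makes the Appendix 1 form a scheduled safety tool: "A questionnaire (see Appendix 1) will be administered at each subsequent visit and at 3, 9 and 12 months to assess for serious adverse events". Section 7.5.3 gives the timing of the Medical and Behavioral History Questionnaire: "It is completed at baseline, three, six, nine and 12 months". Table 7.6.2 shows the same five time points.

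The follow-up version of the form carries several reference periods:

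- The instruction at the top asks about "any of the following conditions SINCE YOU LAST COMPLETED THIS QUESTIONNAIRE".
- The Yes/No column is headed with the past 3 months. The heading is broken in the extracted text but recoverable. The baseline form's heading is broken in the same way, and there the instruction spells out its 2-month period in full.
- Item 9 uses another anchor: "Has your child had any abnormal blood tests since their last visit".
- Items 30 to 32 have no limit. Item 30 reads "Has your child ever had cancer" and item 32 reads "Has your child ever had any unexplained masses or growths".

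On timing, the note under table 7.6.1 reads "Safety and return assessments should be performed within a month of the indicated time point". Table 7.6.2, where this questionnaire is listed, shows no window. No section says which look-back a parent should use.

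**The concern.** A parent who reads the instruction and a parent who reads the column heading answer different questions unless the previous form was completed exactly 3 months earlier. If the interval is longer, the column leaves out the oldest part of it. If it is shorter, the column reaches back into time the previous form already covered. The form provides one shared free-text space for explaining Yes answers and no field for onset dates, so nobody can tell afterwards which period an answer refers to.

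The form asks about fevers (item 1), infections (item 2) and hospitalisation (item 33). Infections are part of the primary safety outcome in sections 4.1 and 8.5. After the contact at days 7-10, section 8.5 lists infection assessment only at 6 and 12 months, so this questionnaire is the named source for the time between. With 12 children, one child wrongly classified moves an incidence by 1/12 = 8.3 percentage points.

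**Working it through.** The documents give no figure to reproduce here. The check is interval arithmetic.

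**Inputs**

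- Look-back under the column heading: 3 months (Appendix 1, follow-up form).
- Form dates: 0, 3, 6, 9 and 12 months (sections 7.5.3 and 7.6.2).
- Window: plus or minus 1 month. This is an assumption for this form, because the sentence stands under table 7.6.1.
- Other early contacts: day 1 and days 7-10 (section 6.6).

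**Formulas.** Let d be the months between two consecutive completed forms. For a parent who answers by the column:

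- unasked time = max(0, d − 3)
- overlap = max(0, 3 − d)

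For a parent who follows the instruction, both are 0 for any d, provided a later form is completed.

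**Results under the column heading**

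| Case | Form dates (months) | d | Unasked | Overlap |
|---|---|---|---|---|
| On schedule | 3 and 6 | 3 | 0 | 0 |
| Month-9 form missed, nominal dates | 6 and 12 | 6 | 3 (months 6 to 9) | 0 |
| Early form, then late form (window) | 2 and 7 | 5 | 2 (months 2 to 4) | 0 |
| First follow-up form late (window) | 0 and 4 | 4 | 1 (months 0 to 1) | 0 |
| Late form, then early form (window) | 4 and 5 | 1 | 0 | 2 |
| Month-3 form missed, next form late (window) | 0 and 7 | 7 | 4 (months 0 to 4) | 0 |
| Month-6 form missed, early then late (window) | 2 and 10 | 8 | 5 (months 2 to 7) | 0 |

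In the fourth case the day-1 and day 7-10 contacts cover the first days. What remains unasked is about day 10 to day 30 after the infusion. In the sixth case the same contacts cover the first 10 days or so of the 4 months.

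Only the second row is independent of the window assumption. A missed month-3 or month-6 form on nominal dates gives the same result: 6 − 3 = 3 months.

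Item 9 agrees with the other two periods only if a visit is taken to mean the time point of the previous form. If it means an in-person visit, the 12-month form reaches back to month 6, which is 12 − 6 = 6 months even on schedule.

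**The case against.** The strongest reply is that the gap is conditional. It needs a late or missed form, an event in the uncovered stretch, a parent who follows the column rather than a capitalised instruction, and no other contact that picks the event up. At nominal spacing it is zero. That is correct, and the documents give no basis for a likelihood. It limits the size of the point, but the form still asks conflicting questions.

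Other collection also exists. Section 9.2 requires all adverse events reported or observed from the infusion to be recorded, section 9.4 draws on any data collected, and there is a history and physical at 6 months. These may catch some events. They are less likely to reveal a fever or infection that has resolved and that nobody asks about. It also stands that section 6.6 gives the form's purpose as serious adverse events and that section 8.5 does not name the form. Its link to the infection endpoint is therefore inferred from its items.

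A reader might go further in three ways that the documents do not support:

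- **That incidences must come out too low.** Early forms overlap by up to 2 months and can report one event twice, so the error in event counts can go either way.
- **That masses or tumors could fall into the gap.** Items 30 to 32 ask about any time, and the baseline form asks the same three items in the same words. A change from No to Yes shows new onset. Only a child already positive at baseline is ambiguous, and the explanation space can address that.
- **That this form is the only scheduled safety instrument at 3, 9 and 12 months.** Section 2.8 plans remote safety assessments at 3 and 12 months, section 7.1 a remote safety assessment at 12 months, and table 7.6.1 blood tests at 12 months. Some of these may be the same form, but the documents do not say so.

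**Conclusion.** The point holds as a conflict of wording in a named safety questionnaire, with consequences in both directions. On nominal dates, one missed interim form leaves 3 months unasked for a parent who answers by the column. This rests only on the published schedule and the column heading. If the one-month window is assumed to apply, the gap can reach 2 months with no form missed, and 4 to 5 months with one missed. The overlap can reach 2 months. Applying the window is reasonable, because Appendix 1 is titled as the safety questionnaire and section 6.6 places it in safety follow-up, but it remains an assumption.

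The gap is possible rather than certain, and its frequency cannot be estimated from the documents. It mainly affects transient fevers, infections and hospitalisations. No sample size or error rate is involved. The change should be made because it costs little and the form asks about a component of the primary safety outcome.

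**What to change.** Use one look-back throughout the follow-up form. Change the column heading and item 9 to match the instruction, so that all three refer to the time since the form was last completed. Have staff enter the date of the last completed form, or the infusion date for the first follow-up form. In the existing explanation space, ask for the onset date of each Yes, so that overlapping reports can be de-duplicated and events placed relative to the infusion. Items 30 to 32 need no change to close the gap.

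The cost is a revised form, IRB notification and one date filled in per form. No visit, item or participant is added. With this change the unasked time is zero for any timing or any missed interim form, provided a later form is completed.
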